(i) Inclusion criteria: a) 20-35 weeks pregnant, b) Living with HIV, c) currently prescribed ART.

332
333 (ii) **Exclusion criteria:** a) High-risk pregnancy for reasons other than HIV status (e.g., pregnancy complications, preeclampsia, gestational diabetes, preterm labor), b) Self-reported participation in another ART adherence-related intervention study, c) Unable to understand consent process, and d) Planning on relocating out of Nyanza province in the following 12 months.

334 (c) **Sampling**

335 (i) **Sample size determination:** Sample size determinations are based on standardized feasibility procedures outlined in the literature.⁷⁸⁻⁸⁰

336 (ii) **Sampling procedures:** We will recruit 40 pregnant women from 2 designated clinics. 20 women will be recruited from Lumumba sub-County Hospital to participate in our intervention. During the same period, 20 women will be recruited from Kisumu County Hospital to participate as our control group. We have opted to use an alternate clinic site for the control group not receiving cash transfers to avoid interactions between women receiving cash transfers and women not receiving cash. We will recruit in-person, with a clinic staff member positioned in the clinic waiting room. Interested women will be assessed for eligibility using a brief screening assessment administered by a female study staff member. For women who are eligible, the staff member will privately give a more complete description of the study, and if the individual is interested, the consent process will begin.

337 (d) **Procedures**

338 (i) **Description of the intervention pilot test:** To test feasibility, we will recruit and enroll N= 40 women, 20-35 weeks pregnant, 18-years and above, living with HIV (n=20 for the intervention group and n=20 for the control group).

339 **Intervention group (n=20):** Women in the intervention group will receive personalized support for breastfeeding provided by a local skilled lactation specialist and a monthly UCT of 10,000KES.

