Phase Two: The key informant interviews and focus group discussions will provide us with feedback on a proposed intervention. Thus, data collected from these activities will be qualitatively reviewed and used to make modifications to the intervention before pilot testing. Content analysis⁸¹ for the focus group discussions will be applied to coding and analysis using dedoose software. The focus of the analysis for the data collected during pilot testing will be to assess the impact of the intervention on measures such as depression, financial security, relationships, stress, empowerment, social support and adherence to PMTCT guidelines as well as to gather feedback from the women who participated in the intervention. Published scales will be scored according to the scales' guidelines. Although our sample size may be too small to detect statistically significant differences, we will use statistical analysis to look for difference/trends in scores across time within each group (intervention and control), as well as differences between the intervention and control group scores at each timepoint. After the pilot is complete, we will conduct exit interviews with participants in the intervention group to assess the acceptability of all intervention components and suggestions for improvement. Transcripts from these interviews will be coded and content analysis⁸¹ will be used to group and summarize women's feedback regarding the intervention. Documentation from the lactation specialist will be analyzed using a longitudinal qualitative approach to determine the specific barriers or successes women experienced with regards to optimal infant feeding across time. The analysis will also identify what information, support or treatments were offered and to what extent women were able to overcome these barriers given the personalized care provided.

10. TIME FRAME/DURATION OF THE PROJECT:

Months	Year1		Year 2		Year 3		Year 4		Year 5	
	1-6	6-12	1-6	6-12	1-6	6-12	1-6	6-12	1-6	6-12
Operationalize study procedures										
Hire & train researchers										
Recruit participants and data collection Phase 1										
Process data from Phase 1										
Intervention development										
Recruit key informants/ focus group participants and initial data collection for Phase 2										
Revise and finalize intervention										
Phase 2 Pilot test of the intervention										
Process data from Phase 2										

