For the Intervention Pilot Test: The lactation specialist who will be providing personalized lactation support will be trained on the protection of human subjects including maintaining privacy and handling personally identifiable information. The financial administrators facilitating the UCTs will also be trained and they will only be given the information about participants necessary for administering the monthly UCTs. A potential risk of the cash transfer is women could experience negative feelings including stress, anxiety or sadness if they are asked to or forced to share some or all of the money with their partners or others in their household/ community. We will assure women that no information about the monthly UCTs will be disclosed to anyone outside our study team. In addition, if women do not have access to a telephone of their own, we will provide them with a telephone for use to ensure to the extent possible the money will be privately and directly available to them. We will also monitor closely including via monthly follow-up phone calls with participants to promptly identify and address any adverse events experienced by women related to the monthly UCTs. Cash transfers have been used widely in a variety of settings to include similar sums of money without negative consequences to recipients. We will also discuss the progress of our study regularly with clinic staff at our research sites to identify any real or potential negative impact related to the intervention. To reduce risk of any negative interaction between our intervention and control arms we will be using two separate, but matched, clinics. In this way we attempt to avoid a potential situation where women in the control group discuss their participation in the study with women in the intervention group and vice versa leading to the control group to feel negatively about the study or members of the intervention group as they are not receiving the same supportive intervention.

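### The pilot analysis sets out to assess the intervention's impact from arm differences, but each arm is a single clinic and allocation is not randomised, so arm and clinic cannot be separated

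*Protocol*

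**What the plan says.** **Analysis (Protocol 9(b)i, Phase Two).** "The focus of the analysis for the data collected during pilot testing will be to assess the impact of the intervention" on a list of outcomes that includes depression, stress, financial security and adherence to the PMTCT guidelines. The methods are within-group trends over time and "differences between the intervention and control group scores at each timepoint". The one reservation is "Although our sample size may be too small to detect statistically significant differences".

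**Recruitment (Protocol 8, Intervention Pilot Test, (c)(ii)).** "20 women will be recruited from Lumumba sub-County Hospital to participate in our intervention", and over the same period "20 women will be recruited from Kisumu County Hospital to participate as our control group". The reason is given openly: "We have opted to use an alternate clinic site for the control group not receiving cash transfers", so that women who receive cash and women who do not are kept apart. No randomisation of women or of clinics is described.

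**Matching (Protocol 11(a1), Intervention Pilot Test).** "we will be using two separate, but matched, clinics". No matching variables are named, and the sentence concerns avoiding friction between the arms.

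**Aim.** The Abstract and sections 7a and 7b give the purpose as acceptability and feasibility, and section 8 (d)(i) agrees: "To test feasibility, we will recruit and enroll N= 40 women". Section 7b also speaks of potential impact, a softer wording than that in 9(b)i.

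**The concern.** With one clinic per arm, any difference between the hospitals is carried in full into the arm comparison. Such differences could lie in the women who attend, the local economy, the counselling offered or the quality of records. The stated focus of the analysis is therefore an effect that the design cannot isolate.

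The caveat about sample size is true, but it describes a different problem. It suggests that more women would settle the question, whereas more women from the same two clinics would only estimate the mixed quantity more precisely.

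Followed as written, a difference in PMTCT adherence, depression or financial security could be reported as the impact of cash plus lactation support when part or all of it is a difference between clinics.

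**Working it through.** **No figure to reproduce.** The pilot sample size rests on feasibility literature. The protocol gives no alpha, power, effect size, SD or ICC.

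**Structure.** There are 2 clinics and 2 arms, so 2 − 2 = 0 degrees of freedom remain for clinic variation within arm. Clinic variance cannot be estimated from these data, and the arm indicator and the clinic indicator are the same variable.

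**What the baselines can remove.** Protocol Table 3 has baseline values for depression, stress, food insecurity, financial status, relationships, social support and empowerment, and also for viral load and prenatal breastfeeding self-efficacy. Stable clinic differences on these can be seen and adjusted for. Two things remain:
- Changes over time that are specific to a clinic.
- Exclusive breastfeeding and infant prophylaxis. These are two of the three PMTCT pillars in the Abstract; they begin after birth and have no baseline value. 

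Within-group trends do not help, because they mix the intervention with the ordinary course from pregnancy to six months postpartum.

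**Illustration of size.** Assumptions, none from the protocol: ICC 0.01, 0.05 or 0.10; total outcome SD of 1; two-sided 5% two-sample t-test on a follow-up score; no true effect; clinics treated as draws from a population of clinics. Let *s* be the share of clinic variance left after matching (1 = no benefit, 0.5 = halved).

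- Variance inflation: f = 1 + n·s·ICC/(1 − ICC)
- False-positive rate: 2·P(T > t₀.₉₇₅/√f), with 2n − 2 degrees of freedom
- Example, n = 20, s = 1, ICC 0.05: f = 1 + 20 × 0.05/0.95 = 2.053. With 38 degrees of freedom t₀.₉₇₅ = 2.024, and 2·P(T > 2.024/√2.053) = 16.6%.

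| Women per arm | s | ICC 0.01 | ICC 0.05 | ICC 0.10 |
|---|---|---|---|---|
| 20 | 1 | 7.3% | 16.6% | 26.6% |
| 20 | 0.5 | 6.1% | 11.0% | 17.2% |
| 100 | 1 | 16.6% | 43.2% | 57.2% |
| 100 | 0.5 | 11.0% | 30.2% | 44.2% |

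Simulation with 200,000 runs agreed to within about 0.1 percentage points.

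**The two errors compared.** Sampling SE = √(2(1 − ICC)/n); SD of the unmatched clinic difference = √(2·ICC).

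| In outcome SDs | ICC 0.01 | ICC 0.05 | ICC 0.10 |
|---|---|---|---|
| Sampling SE, 20 v 20 | 0.31 | 0.31 | 0.30 |
| Sampling SE, 100 v 100 | 0.14 | 0.14 | 0.13 |
| Clinic SD, any n | 0.14 | 0.32 | 0.45 |

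At 20 v 20, random error is the larger at ICC 0.01, about equal at 0.05 and the smaller at 0.10. More women shrink the first error and leave the second unchanged.

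**Change from baseline, 20 v 20.** With an assumed within-woman correlation of 0.5 and a time-specific share *q* of clinic variance, f = 1 + 20 × (2q·ICC)/(2 × 0.5 × (1 − ICC)). If clinic differences are fully stable (q = 0), the false-positive rate is 5.0%. If q = 0.25, f reduces to 1 + 10·ICC/(1 − ICC), the same expression as for s = 0.5, so the rates are again 6.1%, 11.0% and 17.2%.

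**The case against.** The strongest reply has five parts.

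- **The plan is tentative.** It says it will look for differences and trends, concedes low power, and fixes no test or decision rule. This is fair, but the sentence that sets the focus is unqualified, and the caveat offered is not the one needed.
- **Adjustment and intervals belong in the SAP.** Their absence from the protocol is indeed no fault. The fault is the stated inference, which no SAP could rescue, because no model separates two variables that coincide.
- **Design and mitigation.** Separate clinics guard against contact between arms, the clinics are called matched, and nearly every scale named in 9(b)i has a baseline. All of this stands. The two-clinic choice is defensible, and matching one pair may reduce confounding, but it cannot remove it or make it estimable.
- **Impact is within the aims.** Hypothesis 2 expects support to improve adherence, and section 7b mentions potential impact. Measuring these outcomes is therefore legitimate. What goes too far is dropping the qualifier and attributing the arm difference to the intervention.
- **The numbers are assumed.** They are. They average over hypothetical clinics, whereas here there is one fixed, unknown difference between two chosen hospitals. The 100 v 100 case is not a proposed design, and the q = 0.25 change-score rates are not independent evidence. The figures show that the two limitations behave differently; they do not measure the bias in this pilot.

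**Conclusion.** The concern holds, with high confidence, and should be fixed. Arm and clinic coincide completely, so the between-arm comparison in 9(b)i cannot support a statement about the intervention's impact, and the sample-size caveat does not cover this. That conclusion follows from one clinic per arm without randomisation and needs no numerical assumption.

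The size of the bias is unknown and cannot be estimated from the pilot. It could be smaller than random error at 20 per arm. For scales with a baseline, adjustment can deal with stable clinic differences. For exclusive breastfeeding and infant prophylaxis it cannot use a prior value of the outcome.

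**What to change.** In 9(b)i, Phase Two, replace the statement that the focus is to assess impact with wording such as:

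> *The analysis will describe acceptability and feasibility, and will estimate descriptively the between-arm differences, with 95% confidence intervals and adjusted for the baseline value where one is collected, in* [existing list of measures].

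Then add:

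> *Because each arm is one clinic without random assignment, these differences combine clinic and intervention effects. The confidence intervals reflect the sampling of women only. The differences will not be interpreted as intervention effects. Exclusive breastfeeding and infant prophylaxis have no baseline to adjust for.*

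Keep the small-sample caveat, the within-group trends, the exit interviews and the analysis of the lactation specialist's notes. The stated focus then agrees with the acceptability and feasibility objective. Hypothesis 2 and the potential-impact wording in 7b should be read subject to the same limit.

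**Cost.** Wording in one paragraph. No extra women, visits or data are needed, since the baseline measures are already collected in both arms. The price is that the pilot cannot claim an intervention effect from the arm comparison.

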396 care for the participant and her infant (see also Table 3). At each research encounter, participants in both the
397 intervention and control groups will be reimbursed for their transportation costs and provided with refreshments.
398

399 For participants in the intervention group, the lactation specialist will coordinate to meet women, whenever
400 possible, on the same day of their research encounters with our Research Associate who will collect survey data and
401 infant weights. To the extent possible, we will also arrange the research encounters to coincide with participants
402 regular clinic visits. Following each session with participants, the lactation specialist will write or dictate a summary
403 note to include her professional assessment with regards to the adequacy of the participants milk supply, her
404 assessment of the woman's breastfeeding practices (i.e. to what extent women are exclusively breastfeeding and/or
405 any successes or challenges women experience), and a summary of the counseling or treatment she provided.

406 Women from the intervention group will also be asked to participate in exit interviews, conducted at around
407 6-months postpartum, to assess the acceptability of all intervention components and to seek suggestions for
408 improvement. An interview guide for the follow up interviews has been submitted for IRB approval along with this
409 updated protocol.

410 Table 3

	Baseline: recruitment	Birth: no face-to-face encounter	2-weeks	4-weeks	6-weeks	3-months	6-months
Demographic and Individual item Questions							
Baseline questionnaire	x						
Breastfeeding focused follow-up questionnaire		x	x		x		
6-week follow-up questionnaire					x		
6-month follow-up questionnaire V 1.1							x
SCALES							
Mental Health: PHQ-9; Perceived stress scale	x				x		x
Food Insecurity: Household food insecurity access scale	x				x		x
Financial status: Wealth Index	x				x		x
Relationships: Couples Satisfaction Index	x				x		x
Breastfeeding: Prenatal BF Self-Efficacy (pre) Postpartum Breastfeeding Self Efficacy (PP)	x(pre)		X (PP)	X (PP)	X (PP)	X (PP)	X (PP)
Social support: The Duke-UNC Functional Social Support (DUFSSQ)	x				x		x
Empowerment: Demographic Health Survey Household decision making and IPV	x				x		x
HIV related stigma: 12-item HIV stigma scale	x				x		x

411	Infant weight measured by RAs		x	x	x	x	x
412	From participant's clinical record: hemoglobin, Viral Load	x				x	x

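### The pilot aims to assess impact, but neither quantitative comparison it names carries a baseline gap between two non-randomised clinics into the follow-up contrast between arms

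*Protocol*

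**What the plan says.** Protocol section 9(b)i (Data analysis, Phase Two) sets the focus of the pilot analysis: to "assess the impact of the intervention on measures such as depression, financial security, relationships, stress, empowerment, social support and adherence to PMTCT guidelines". It concedes that the sample may be too small for statistical significance. It then names two quantitative comparisons, which will look for differences or trends "in scores across time within each group (intervention and control), as well as differences between the intervention and control group scores at each timepoint".

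Section 8, Intervention Pilot Test, (c)(ii) allocates by site: "20 women will be recruited from Lumumba sub-County Hospital to participate in our intervention". The 20 controls come from a second hospital over the same period, so that women who receive cash and women who do not are kept apart. Section 11(a1) says "we will be using two separate, but matched, clinics" but gives no matching variables.

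Table 3 in section 8 schedules the scales in both arms at baseline, 6 weeks and 6 months. This covers the row "Mental Health: PHQ-9; Perceived stress scale" and also food insecurity, wealth, couples satisfaction, social support, empowerment and stigma. Breastfeeding self-efficacy is the exception: the instrument changes after birth ("Prenatal BF Self-Efficacy (pre) Postpartum Breastfeeding Self Efficacy (PP").

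The protocol nowhere names a between-arm comparison of change, a group-by-time term, or adjustment for the baseline score.

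**The concern.** With one clinic per arm and no randomisation, a difference between the two groups of women at enrolment is foreseeable. The two named comparisons handle it badly.

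- **Trends within each group** use the baseline score but have no comparator. Scores can change between pregnancy and 6 months postpartum in both groups, so a trend in one arm is not an intervention effect. A trend that is significant in one arm and not in the other is not a test between arms.
- **Differences at each timepoint** compare the arms, but at 6 weeks and 6 months they use follow-up scores only. Whatever remains of the enrolment gap is counted as effect, or masks one.

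The small-sample caveat concerns imprecision. It does not cover bias, and a reader planning a larger trial from these estimates would not be warned of it.

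**Working it through.** The plan states no effect size, SD, alpha or power for the pilot, so there is no figure to reproduce. What follows is an illustration.

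**Inputs.** From the protocol: n = 20 per arm. Assumed: baseline clinic gap g = 0.3 to 0.5 SD, baseline-to-follow-up correlation r = 0.5 to 0.7, two-sided 5% level, no true effect, within-arm SD 1. Two cases for the gap at follow-up: it persists (stays g) or it regresses (shrinks to r × g).

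**Formulas (SD units).**

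- Follow-up scores alone: bias g (persists) or r·g (regresses); SE = √(2/20) = 0.316.
- Baseline-adjusted: bias (1−r)·g or 0; SE ≈ √((1−r²)·2/20), which is 0.274 at r = 0.5 and 0.226 at r = 0.7.
- Difference in change: bias 0 or −(1−r)·g; SE = √(2(1−r)·2/20), which is 0.316 at r = 0.5 and 0.245 at r = 0.7.

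**Results** (100,000 simulated trials per scenario; bias in SD, then false-positive rate):

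| g | r | Gap | Follow-up alone | Baseline-adjusted | Change |
|---|---|---|---|---|---|
| 0.3 | 0.5 | regresses | 0.15, 7.6% | 0.00, 5.0% | −0.15, 7.4% |
| 0.3 | 0.5 | persists | 0.30, 15.0% | 0.15, 8.2% | 0.00, 5.0% |
| 0.3 | 0.7 | regresses | 0.21, 10.0% | 0.00, 5.0% | −0.09, 6.5% |
| 0.3 | 0.7 | persists | 0.30, 15.2% | 0.09, 6.6% | 0.00, 5.0% |
| 0.5 | 0.5 | regresses | 0.25, 12.1% | 0.00, 5.1% | −0.25, 12.1% |
| 0.5 | 0.5 | persists | 0.50, 33.7% | 0.25, 13.4% | 0.00, 4.9% |
| 0.5 | 0.7 | regresses | 0.35, 19.1% | 0.00, 5.0% | −0.15, 9.0% |
| 0.5 | 0.7 | persists | 0.50, 33.8% | 0.15, 9.5% | 0.00, 5.1% |

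A normal approximation with the SEs above agrees closely. At g = 0.5, r = 0.5 with the gap persisting, it gives 35%, 15% and 5%.

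**Precision.** Effective n per arm = 20 × Var(follow-up alone) / Var(method). Simulated with the gap present, this is 24.2 to 37.4 for baseline adjustment, 23.6 to 36.2 with gestational age also in the model (20,000 trials), and 19.9 to 33.5 for change.

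**Would the gap be noticed at baseline?** A t-test with 20 per arm flags a true gap of 0.3 SD 15.2% of the time and one of 0.5 SD 33.8% of the time.

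**Chance imbalance.** If the clinics were truly alike, the observed gap would still have SE 0.316 SD. It would reach 0.3 SD with probability 0.343 and 0.5 SD with probability 0.114.

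**Why gestational age.** Enrolment runs from 20 to 35 weeks. Assuming delivery at 40 weeks, the interval from baseline to the 6-week visit runs from 40 − 20 + 6 = 26 weeks down to 40 − 35 + 6 = 11 weeks.

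**The case against.** - **The sentence names contrasts, not models.** It does not exclude adjustment, and a SAP not at hand may supply it. This is fair as far as it goes. But the protocol does name its comparisons, and as written they are of scores at each timepoint. In this design the baseline needs to be part of the stated comparison.
- **Each timepoint includes baseline.** A reader could subtract the baseline gap from the follow-up gap, whether or not it is significant. That stands for the point estimate. The subtraction has no standard error unless the within-woman correlation is used, and the plan does not name it as the contrast.
- **Chance imbalance is not bias.** This stands. If the clinics are alike, the follow-up contrast is unbiased over repeated trials, so the chance-gap figures support only the precision argument.
- **This is a feasibility pilot with no decision rule tied to the scores.** This also stands and limits the weight of the false-positive rates. It does not remove the bias in the estimates of an analysis whose stated focus is impact.
- **Preferring adjustment to change is a matter of taste.** In the table their worst cases are similar: 0.25 SD in opposite directions, 13.4% against 12.1%. For intact clinics a persisting gap is plausible, and there change is the unbiased method. However, for any r between 0 and 1 the adjusted contrast is less biased than follow-up alone in both cases. Below r = 0.5 the change contrast can be worse: at g = 0.5, r = 0.3 with regression, its bias is −0.35 SD against 0.15 SD for follow-up alone. Reporting both meets the point.
- **The reach is limited.** Exclusive breastfeeding has no baseline value, and no model separates clinic from intervention with one clinic per arm. Both are true.

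**Conclusion.** The concern holds. Followed as written, the follow-up contrast between arms absorbs a clinic gap present at enrolment, although the data to reduce that bias are already scheduled. Under the assumed inputs, baseline adjustment gave less bias and fewer false positives than follow-up scores alone in all eight scenarios.

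The direction of this result follows from the design. The size rests entirely on the assumed gap and correlation, and on the gap either persisting or shrinking to r × g. If the clinics follow different time courses for other reasons, none of the three methods corrects it. This should be changed, but it does not undermine the feasibility and acceptability aims.

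**What to change.** Reword the comparison sentence in section 9(b)i along these lines:

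- For each scale measured at baseline, 6 weeks and 6 months, the between-arm comparison is a longitudinal model with arm, visit, arm-by-visit, baseline score and gestational age at enrolment, allowing for within-woman correlation. Report the adjusted arm difference with a 95% confidence interval at 6 weeks and at 6 months, as exploratory.
- Give the difference in change from baseline as a sensitivity analysis, and say that each method is unbiased under a different assumption about the gap.
- Show within-group trends descriptively.
- State that adjustment reduces but cannot remove clinic confounding with one clinic per arm.
- State that postpartum-only outcomes such as exclusive breastfeeding have no baseline of their own. For breastfeeding self-efficacy, use the prenatal score as a covariate only, because a change score across two instruments has no clear meaning.

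The cost is one reworded sentence, slightly more analysis, and one or two degrees of freedom with 40 women. No visit, instrument or participant is added. Gestational age at enrolment is not listed in Table 3, but it must be known to apply the eligibility criterion, so it only needs to be kept in the dataset.

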The pilot test will be carried out among 40 pregnant women divided into 2 groups (n=20 intervention group, n=20 control group). The intervention group will receive personalized lactation support and monthly UCTs from approximately 30 weeks pregnancy to approximately 6-months postpartum. Personalized lactation support will be provided by a local, experienced lactation consultant. Her support will be aimed at providing person centered care to assess for and address barriers to optimal, safe infant feeding with a focus on exclusive breastfeeding for the first 6-months postpartum. The cash transfer will be 10,000 Kenyan shillings per month. This amount is slightly less than the median amount women in our preliminary study reported needing to meet their basic needs (13,500KES) and is in line with other cash transfers completed in the area.⁸³ It is equivalent to approximately 3.33USD per day, or about 40% more than the World Bank's most recent poverty line estimated of 1.90 USD per person per day. This amount is lower than the estimated median

182 monthly income for those informally employed in sectors such as retail trade or food service in Kenya
183 (estimated at 15,000 and 30,000KES monthly in rural and urban areas respectively).⁹¹ We expect this amount
184 will allow women to meet many of their household's basic needs during late pregnancy and throughout the
185 period of EBF when women are largely unable to maintain gainful employment.

186 The control group will receive the current standard care.
187

188 We will recruit women during their 20th-35th week of pregnancy and follow them until 6-months postpartum.
189 We will collect survey and clinical data at baseline (20-35 weeks pregnancy, 2-weeks, 4-weeks, 6-weeks, 3-
190 months and 6-months). We will conduct qualitative interviews at the end of the intervention period with all 20
191 participants in the intervention group to evaluate the acceptability of the pilot intervention as well as to
192 better understand how UCTs were used and the perceived impact on financial security, food security, mental
193 health, relationships with primary partners and the ability to adhere to PMTCT strategies.
194

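### A 20-per-arm feasibility pilot is analysed as an unranked search for impact over 21 to 23 arm comparisons, with a caveat that covers only missed effects

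*Protocol*

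**What the plan says.** Section 7b sets the pilot's objective as testing acceptability and feasibility. The sample size section of the Intervention Pilot Test agrees: "Sample size determinations are based on standardized feasibility procedures". It gives no effect size, standard deviation, significance level or power. The arms are "n=20 intervention group, n=20 control group" and are formed by clinic, not by randomisation: "20 women will be recruited from Lumumba sub-County Hospital to participate in our intervention", with the controls recruited at a second hospital.

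The Phase Two paragraph of section 9(b)i takes a different emphasis. The focus of the pilot analysis "will be to assess the impact of the intervention on measures such as depression, financial security, relationships, stress", followed by further measures that end with adherence to PMTCT guidelines. The list is illustrative, so it is open. Within each arm, the plan is to search for changes over the visits. Between arms, it covers every visit: "as well as differences between the intervention and control group scores at each timepoint". The one statistical caution is "Although our sample size may be too small to detect statistically significant differences".

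Table 3 shows when each scale is given. All except breastfeeding self-efficacy are given at baseline, 6 weeks and 6 months only. Breastfeeding self-efficacy has a prenatal form at baseline and a postpartum form at all five postpartum visits.

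**The concern.** The paragraph commits to many comparisons, ranks none of them, and describes the exercise as an assessment of impact. A reader is told what to think if nothing shows (the sample was small) but not what to think if one scale differs at one visit. With this many looks at 20 women per arm, an isolated difference is an ordinary chance event, and the small sample ensures that any difference large enough to be called significant looks large.

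Two features add to this. Each arm is a single clinic, so a difference may reflect the clinic. A trend within one arm cannot separate the intervention from the usual course between late pregnancy and 6 months postpartum. What is at stake is whether the pilot's statements on impact rest on a defined question or on whichever result stands out.

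**Working it through.** The protocol gives no power, significance level or effect size, so there is no figure to reproduce. Two-sided 5% per comparison is assumed throughout.

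**Number of comparisons (Table 3).**
- Scores collected at 6 weeks and 6 months: PHQ-9, perceived stress, food insecurity, wealth index, couples satisfaction, social support, empowerment and HIV stigma. That is 8 scores, or 9 if household decision making and partner violence, which share the empowerment row, are scored separately.
- Breastfeeding self-efficacy: 5 postpartum visits.
- Post-baseline comparisons between arms: 8 × 2 + 5 = 21, or 9 × 2 + 5 = 23.
- Not counted: baseline comparisons (which would give 30 to 33), within-arm trends (9 or 10 measures in 2 arms, so 18 to 20), infant weight, viral load and feeding practice.

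**Chance of at least one nominally significant arm difference when nothing differs.** Expected number: 21 × 0.05 = 1.05 to 23 × 0.05 = 1.15. Under independence the chance is 1 − 0.95^k, which gives 0.66 for k = 21 and 0.69 for k = 23. Correlation lowers it. Simulated two-sample t-tests with 20 per arm gave:

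| Correlation between scales / within a scale over time | 21 comparisons | 23 comparisons |
|---|---|---|
| 0 / 0.5 | 62% | 66% |
| 0.3 / 0.5 | 57% | 60% |
| 0.5 / 0.5 | 50% | 53% |
| 0.5 / 0.7 | 46% | 48% |

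In this table, different scales at different visits are correlated by the product of the two values. If instead every pair of comparisons has the same correlation, the chance is 56–58% at 0.3 and 44–46% at 0.5. The overall range is roughly 45% to 70%. One prespecified scale at one visit would carry 5%.

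**Smallest significant difference.** t(0.975, 38 df) × √(2/20) = 2.024 × 0.316 = 0.64 SD. With 16 per arm it would be 0.72 SD.

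**Size of a significant result.** From 200,000 simulated comparisons per row, 20 per arm; the last column is the mean absolute estimate among significant results divided by the true effect:

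| True effect (SD) | Power | Mean estimate if significant (SD) | Ratio to truth |
|---|---|---|---|
| 0.2 | 9% | 0.75 | 3.8 |
| 0.3 | 15% | 0.78 | 2.6 |
| 0.4 | 24% | 0.80 | 2.0 |
| 0.5 | 34% | 0.83 | 1.7 |
| 0.8 | 69% | 0.96 | 1.2 |

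With no true effect, a significant result averages 0.72 SD. Power reaches 80% only at a true effect of about 0.89 SD (normal approximation).

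**The case against.** The strongest reply is that section 9(b)i promises little. It mentions significance only to disclaim it, states no test, level or decision rule, and already presents the comparisons as underpowered. Multiplicity handling is commonly left to an analysis plan, which is not shown. All of this stands, and the absence of a multiplicity method is not the point here. The point is what the protocol does state: impact as the focus, an open unranked list, and a caution in one direction only.

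The assumption of no true effect on any scale can also be challenged, since the intervention arm receives a monthly cash transfer. Suppose wealth index and food insecurity truly shift at both visits. Then 17 to 19 null comparisons remain, and the independent-case chance is 1 − 0.95^17 = 0.58 to 1 − 0.95^19 = 0.62. That is lower but still large. The 5% level also presumes comparable arms, which allocation by clinic does not secure.

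Confidence intervals alone do not cure the problem: among 23 intervals the chance that at least one excludes zero is the same as for 23 tests. That is correct, and it is why labelling as exploratory and reporting every comparison matter more than dropping p-values.

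Finally, adherence to PMTCT guidelines is not a ready-made lead outcome. Section 6 describes three behaviours and Table 3 lists no adherence scale. Its place at the end of an illustrative list says nothing about rank. The fix takes account of this.

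**Conclusion.** The point holds with limits. The protocol makes impact the focus of a feasibility pilot, plans an unranked search over 21 to 23 post-baseline arm comparisons plus within-arm trends, and warns only of missed effects. Given two-sided 5% per comparison, comparable arms and no true effect, the chance of at least one nominally significant arm difference is roughly 45% to 70%. A significant result overstates a true effect of 0.2 to 0.5 SD by about 1.7 to 3.8 times.

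A reader might infer more, and the documents do not support it:
- That a chance finding is more likely than not. This holds under independence and moderate correlation. Under strong correlation it is about even or slightly less, and strong correlation is plausible for linked constructs measured repeatedly in the same women.
- That any significant result would be grossly inflated. At a true effect of 0.8 SD the ratio is only about 1.2.
- That every scale is compared at every visit. Table 3 limits all but one to baseline, 6 weeks and 6 months.
- That the pilot's estimates will size a later trial. No section says so, including section 12 on the use of results. It is a foreseeable misuse, not a stated plan.

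**What to change.** Amend the Phase Two paragraph of section 9(b)i as follows.

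1. State that acceptability and feasibility are the pilot's primary aim, as in section 7b, and that all scale comparisons are exploratory.
2. Report every scale at every visit where it is collected as a between-arm estimate with a 95% confidence interval (half-width about 0.64 SD with 20 per arm). Do not present this as a search for significant differences or within-arm trends.
3. If a lead quantitative outcome is wanted, name one defined component of Hypothesis 2's adherence at 6 months: maternal ART, infant prophylaxis or exclusive breastfeeding. Section 8 already has the surveys collect medication adherence for mother and infant and breastfeeding practice. Adherence to the guidelines as a whole is not a single measured variable, and naming it undefined would leave the same freedom of choice.
4. Extend the caveat: isolated differences among some 20 comparisons may be due to chance or to differences between the two clinics, are likely to be inflated, and should not be read as evidence of impact or used as effect sizes.

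The cost is a few sentences, with no new data collection. The pilot gives up significance claims that it already doubts it can support.
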